5.9.1. Proprietary Device Name: PR3 Ultrasound System

Classification: Ultrasonic imaging system **Regulation Number:** Title 21 CFR 892.1560

Medical Specialty: Radiology

Medical Device Regulatory Class: II (Special Controls)

510(K): K080935

Imagio is similar to the PR3 Ultrasound system in that both systems use ultrasound waves propagating through tissue to obtain images of soft tissue. The diagnostic ultrasound component of Imagio uses the standard parameters of the PR3 Ultrasound system. However, the opto-acoustic part of Imagio employs passive detection of low-amplitude ultrasound waves instead of ultrasound-emissions used by the PR3-USI.

5.9.2. Proprietary Device Name: Candela GentleLASE Laser

Classification: Dermatological Vascular Lesion Laser

Regulation Number: Title 21 CFR 878.4810

Medical Specialty: Dermatology

Medical Device Regulatory Class: II (Special Controls)

510(K): K083207

Imagio is similar to the Candela GentleLASE Laser in that both systems employ pulsed lasers operating in the near infrared spectral range, and both lasers are used for illumination of skin. Both lasers employ a Class IIIB laser, with the Candela GentleLASE Laser providing a higher energy per pulse.

Seno Clinical Study Protocol: PIONEER-01 300176 Rev 8 PIONEER 01 Protocol Amendment 3.2

- **5.10.** Treatments Administered: Not applicable.
- **5.11.** Selection and Timing of Dose for Each Subject: *Not applicable.*

5.12. Method of Assigning Subjects to Treatment Groups

This is a prospective, controlled, multi-center observational study where all subjects undergo a diagnostic ultrasound, to make a biopsy decision, and then are consented. All subjects will then undergo the Imagio evaluation following conventional diagnostic procedures. Thus, there is no randomization.

5.13. Blinding

Subjects will not be blinded to study procedures but will not have access to the Imagio evaluation result.

The investigator will have access to all conventional diagnostic ultrasound, mammography, and biopsy reports, but the interpretation of the Imagio evaluation will not be provided to the investigator. The investigator will also have the option to perform the color or power Doppler during the conventional ultrasound examination for research purposes. The Doppler information will not be used in the analysis of this study for determining the safety and effectiveness of the Imagio.

The 7 independent registration readers and the 3 other independent reimbursement readers per case will have separate access to the relevant images and videos used to make the decision to perform or defer a biopsy in addition to the Imagio diagnostic ultrasound image and opto-acoustic image. Imagio and IUS are regarded as the two most important image sets for comparisons; these will be the image sets to be reviewed by the registration readers. Mammography is regarded as the most likely referral methodology and will be read alone and in combination with CDU and Imagio by the reimbursement readers. Readers will not have access to the background clinical information or to the histopathology report. The Truth Panel will have access to all clinical data, QA evaluator, and independent reader results to be able to alert the study medical monitor regarding any high risk subjects; the Seno study coordinator will in turn alert the study investigator in the event that the subject was not biopsied or the biopsy report was missing.

5.14. Concomitant Therapy: *Not applicable.*

5.15. Restrictions: None

5.16. Treatment Compliance

Imagio will be operated only by study personnel trained by Seno personnel or their representatives. Subject compliance is ensured.

Confidential Page 38 of 80

5.17. Packaging, Labeling, and Instructions for Use

Seno will ship investigational devices to participating sites utilizing packaging materials that protect the investigational devices from potential damage during transit. Seno personnel will unpack and install the study device as well as conduct and document operator training for study personnel.

Imagio will bear appropriate investigational device labeling, to include the statement: "Caution – Investigational Device. Limited by United States Law to Investigational Use." Seno will also provide adequate instructions for use written at a comprehension level appropriate for the operators participating in this study; please refer to Section 5.3.

5.18. Storage and Accountability

Investigators will be responsible for ensuring that only authorized study personnel have access to the investigational device.

6. STUDY PROCEDURES

6.1. Study Procedure Overview

The study procedures and the sequence in which they will occur are defined below in Table 3 below and described in greater detail in Section 6.2:

Table 3: SCHEDULE OF EVENTS

Evaluation	Screening Visit	Enrollment Visit Day 1	Imaging Visit Day 1-10	First Biopsy (within 12 Months)*	Subjects with No Biopsy (12 Months +/- 30 days)**
Informed Consent		Х			
I/E Criteria		X##			
Demographics/ Medical History		Х			
BI-RADS Score (including density)	Х				
Conventional Diagnostic Ultrasound	Х				
Biopsy Decision	Х				
Mammogram	X#				
Imagio Evaluation			X*	X**+	X**+
Subject Questionnaire			Х		
Directed Breast History			Х		
Adverse Event Evaluation			Х	Х	Х
Histopathology Assessment				Х	Х
Histopathology Report				Х	Х
Past Imaging Studies		Х			

[#] Subjects may have a mammogram at investigator discretion.

Subjects must have a conventional diagnostic ultrasound and all other diagnostic tests completed and decision to biopsy made before the Enrollment Visit.

- * Subjects who are scheduled to have a biopsy at any time during the 12 month Follow-Up (including baseline) will have an Imagio evaluation of the breast mass within 30 business days prior to the biopsy; for subjects requiring a second biopsy, additional time (up to 45 business days) will be permitted to perform the second biopsy if a waiver is granted by the study Medical Monitor, but a second Imagio Evaluation is not performed.
- ** Optional 6 month (+/- 30 Days) Follow-Up Visit at investigator discretion and planned 12 month Follow-Up Visit if no biopsy is performed within 12 months of Enrollment Visit.
- + The Follow-Up Visit will also include appropriate diagnostic imaging at the investigator's discretion.

The investigator will check subject eligibility, including prescribed medications. The estimated total time for the Imagio evaluation is approximately 15 minutes depending on breast dimensions, mass location(s), mass size(s), mass type(s) and number of test positions required to fully visualize the mass(es).

6.2. Study Visits

6.2.1 Screening Visit

The following procedures will be conducted at the Screening Visit:

- 1. Qualify subject
- 2. Verify from images and/or reports that a suspicious mass was seen
- 3. Confirm that a conventional diagnostic ultrasound is to be performed or has been performed. The conventional diagnostic ultrasound should be performed prior to consenting the subject.
- 4. Confirm that the subject has an undiagnosed suspicious finding within the previous 45 business days, by palpation or by a screening or diagnostic methodology other than ultrasound

6.2.2. Enrollment Visit, Day 1

The following procedures will be conducted at the Enrollment Visit:

- 1. Verify from mammograms and reports that a suspicious mass was seen
- 2. Confirm that conventional diagnostic ultrasound and all other diagnostic tests were performed
- 3. Confirm that the biopsy decision has been made
- 4. Review HIPAA form and informed consent form with subject and obtain signature; consent to both forms must be obtained prior to performing any study procedures.
- 5. Full assessment of subject eligibility with inclusion/exclusion criteria
- 6. Record demographics and medical history
- 7. Document date of informed consent signature and HIPAA authorization in the eCRF.

Upon completion of the conventional diagnostic ultrasound:

- 8. Determine whether the subject had a conventional diagnostic ultrasound that resulted in a recommendation for biopsy or a recommendation not to biopsy.
- 9. Schedule Imagio evaluation to take place within 10 business days of the Enrollment Visit.

After completion of the Imagio evaluation and prior to the biopsy, the subject will complete the Subject Completed Survey.

Subjects may be asked to return to the clinic to repeat the Imagio scan if (a) the image quality is not acceptable for review by the independent QA evaluators and (b) they have not undergone a biopsy procedure.

Group Determination: For the purpose of subject follow-up activities, subjects will be categorized into the Biopsied Group or Unbiopsied Group. Classification will be determined by the respective site investigator based on the following criteria:

Biopsied Group Criteria:

Has at least one or up to three suspicious solid masses or suspicious complex mixed cystic and solid masses (as either the cause of the clinical or mammographic finding) that the investigator has characterized as either BI-RADS 4 or 5, a biopsy has been recommended for all masses and that subject has agreed to have a biopsy for each suspicious mass that has been identified.

Unbiopsied Group Criteria:

Has at least one solid mass, complex cystic and solid mass, or indeterminate cystic versus solid lesion (as either the cause of clinical or mammographic finding), that the investigator has characterized as BI-RADS 3 or has ≤2% POM, and for which the subject has chosen to have either biopsy or short interval follow-up. If greater than one mass is found and each mass is not recommended for biopsy, then only one mass of the site's choice will be designated as the primary mass and will be followed for up to 12 months; Ideally, the mass with the highest POM as per the investigator will be selected for follow-up.

6.2.3.Imaging Visit(s), Day 1 - 10

Within 10 business days of the completion of the Enrollment Visit and before any scheduled image-guided biopsy, the subject will undergo the Imagio study evaluation. The Imagio evaluation will be performed according to the Imagio Instructions for Use provided for this clinical study. Subjects may be asked to return to the clinic to repeat the Imagio scan if (a) the image quality is not acceptable for review by the independent evaluators and (b) they have not undergone a biopsy procedure. Seno Medical Instruments, Inc. or their designees may be present during the procedures to provide technical support.

The study data will be recorded using electronic data capture (EDC). Any adverse events that occur during this Visit will be entered into the eCRF.

The investigator is to ensure that the site histopathology report is obtained and the relevant results are entered into the eCRF. The central histopathology report will contain cell type, histologic grade for invasive malignant masses and nuclear grade for in situ carcinomas. Additionally, the Sponsor will assign a blinded sonographer to independently determine the maximum diameter of the index mass and extent of disease (which includes not only the maximum diameter of the index mass, but outside-to-outside dimensions between multifocal and/or multicentric invasive disease and/or maximum outside-to-outside largest dimension of combined invasive and in situ disease); the sonographer may be a Sponsor employee without access to diagnosis, histopathology results, reader scores, and nomogram results. Also included will be estrogen, progesterone, and Her-2 receptor status, lymph node status and number of positive lymph nodes. All of these histopathologic prognostic features will be entered into the eCRF. These histopathologic features are known to correlate with biologic behavior of the mass, as will be its OA characteristics. Thus, certain OA features are expected to correlate better with some prognostic histopathologic parameters than with some others.

If the subject does not undergo biopsy of the breast mass within 12 months of enrollment, a subsequent Imagio evaluation will be performed together with any other indicated imaging studies at the 12 month

follow-up Visit. In addition, the Imagio evaluation visit will be conducted prior to any scheduled biopsy that is indicated by interval clinical and/or imaging findings within the 12 month follow-up period.

6.2.4. Follow-up for Subjects with Subsequent Biopsy Within 12 Months Post-Enrollment

Subjects who are scheduled for biopsy because of new interval clinical or imaging findings that present within 12 months of the Enrollment Visit will have an Imagio evaluation in addition to (prior to) the biopsy being performed. The Imagio protocol will be performed according to the Imagio Instructions for Use provided for this clinical study. The study data will be recorded using electronic data capture (EDC). Any adverse events that occur during this visit will be reported. The investigator is to ensure that the histopathology report is obtained and the relevant results are entered into the eCRF.

6.2.5. 12 month Follow-up Visit for Subjects with No Biopsy

For non-biopsied subjects, a second and final Imagio evaluation and any other indicated imaging evaluations will be performed at the 12 month Follow-Up Visit. If an interval clinical and/or imaging problem arises before 12 months that would require a biopsy at that time, an Imagio evaluation and any other indicated imaging studies will be performed (45 days) before the biopsy. Truth Panel confirmation of mass change will be used to establish truth regarding mass changes; if no biopsy is recommended at the Month 12 Evaluation, and if there are no new symptoms, no new physical findings, and no new imaging abnormalities, the subject will be considered to be a True-Negative (TN), subject to truth panel review.

6.3. Study Evaluations and Procedures

6.3.1. Informed Consent

Prior to the initiation of any study activities, written informed consent and HIPAA authorization shall be obtained from all subjects; this will cover any additional data in the event that the subject is to be followed for 12 months and if a biopsy takes place during the subsequent 12 month follow-up. Subjects will authorize the investigator to submit those images used to make the decision to perform a biopsy or to continue follow-up.

6.3.2. Demographics

Demographics will be documented in the electronic Case Report Form (eCRF). This will include date of birth, race, and ethnicity.

6.3.3. Subject Survey

After completion of the Imagio evaluation and prior to the biopsy, the subject will complete the Subject

Data Form.

6.3.4. Adverse Events

Adverse events (AEs) will be collected as outlined in Section 6.5.

6.4. Effectiveness Assessments

Blinded Imagio results will be transferred to the independent ICC that will review all screening and diagnostic imaging conducted including all Imagio results at baseline, prior to any biopsy (i.e. Month 6), and at Month 12 if no biopsy is scheduled. Any imaging studies performed after the Enrollment Visit but before the biopsy will also be forwarded to the ICC for independent reader review.

The histopathology report will be used to establish the diagnosis; if no biopsy is recommended at the Month 12 evaluation, then the Truth Panel will consider all imaging and pathology findings to decide if a True Negative determination can be made. .

6.4.1 Statistical Endpoints

The following statistical metrics are to be determined for each image set relative to the histopathology diagnosis:

- 1. True-positive rate or sensitivity (Se)
- 2. Specificity (Sp)
- 3. Concordance (percent true positive [TP] or true negative [TN])
- 4. Positive likelihood ratio (PLR = Se/(1-Sp))
- 5. Negative likelihood ratio (NLR = Sp/(1-Se))
- 6. Predictive values of a negative test (NPV = TN/(FN+TN))
- 7. Predictive values of a positive test (PPV = TP/(FP+TP))
- 8. Odds ratio (OR = (TP/FP)/ (FN/TN)).

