6.7 Appropriateness of Measurements

Imagio was developed to complement and to add additional knowledge to existing imaging modalities. The selected endpoints (sensitivity, specificity, concordance (percent TP and TN), positive likelihood ratio (Se/ (1-Sp)), negative likelihood ratio (Sp/ (1-Se)), NPV and PPV), and odds ratio give an adequate characterization of the Imagio System in the indications for use by:

- Decreasing the number (percent) of women potentially undergoing biopsy by identifying those unlikely to have a malignant mass while not increasing the number (percent) of false-negative to a clinically unacceptable level (see Non-Inferiority margin discussion).
- Showing that Imagio has a sufficiently high specificity relative to the Imagio ultrasound component.
- Showing that Imagio features differentiate between benign and cancer cases.
- Down classifying BI-RADS 3, 4a, and 4b subjects according to the site investigator.
- Down classifying BI-RADS 3, 4a, and 4b subjects according to IUS.
- Up classifying BI-RADS 3, 4a, and 4b subjects according to IUS

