8.5. Analysis Definitions

The final data for diagnostic test sensitivity and specificity will be presented in terms of a 2×2 table as follows; the threshold for defining a positive POM will be 2% corresponding to clinical practice standards:

Table 5: 2 x 2 Table

	Cancer	Benign
Test +	True Positive (TP)	False Positive (FP)
Test -	False Negative (FN)	True Negative (TN)

The above 2x2 table will also be constructed separately for Imagio and the Imagio diagnostic ultrasound component relative to a cancer or benign diagnosis. In addition, these 2x2 tables will also be generated for immediate biopsies, for delayed biopsies, for all biopsies, and for all cases including those not biopsied; discordant pairs for sensitivity as well as specificity will be analyzed. Those subjects without a biopsy will be excluded if they were not followed without a subsequent clinical evaluation.

A subject will be assigned to a row in the table depending on the respective diagnostic test result. Subjects with a diagnosis (biopsy or 11 month follow-up with no biopsy) will be assigned a column in the table according to the following rules:

- 1. If the result of the biopsy results in a cancer diagnosis, then the subject will be assigned to the Cancer column.
- 2. If the result of the biopsy results in a benign diagnosis, then the subject will be assigned to the Benign column.
- 3. If the biopsy was not performed and the subject was evaluated after 11 months post-baseline (nominal 12 month evaluation), then the subject will be counted as TN as long as there were no contrary clinical or radiologic findings (not to be based on Imagio); any mass declared to have any contrary clinical or radiologic findings will be declared to be a False-Positive if the Imagio POM was ≤2%; otherwise the subject will not be included in the table
- 4. If the baseline Imagio evaluation was not performed or declared to not be useable, then the subject will not be included in the table.

In addition, the cancer group will be further divided into invasive carcinoma and DCIS categories and each of these two categories will be assessed separately within a 2x2 table.

The use of the terms *sensitivity* and *specificity* is justified in this study because the biopsy and 11 month evaluation (12 month nominal evaluation) is the gold standard. The following statistical endpoints will be assessed for each image set:

- The true positive rate (TPR) or sensitivity of the test is defined as TP/ (TP + FN)

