- The specificity of the test is defined as TN/ (TN + FP)
- The concordance of the test is defined as (TP + TN)/N
- The positive likelihood ratio is defined as TPR/FPR
- The negative likelihood ratio is defined as (1 TPR)/(1 FPR)
- The positive predictive value (PPV) is defined as TP/(TP + FP)
- The negative predictive value (NPV) is defined as TN/ (TN + FN)
- The *odds ratio* (OR) is defined as (TP/FP)/(FN/TN)

Given that biopsy decisions are made using the 2% POM, POM levels >2% have limited relevance to the 2% threshold now widely used for making biopsy decisions.

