8.7.4 Other Secondary Analyses

The sensitivity, specificity, concordance, PPV, NPV, PLR, NLR, and odds ratio for Imagio and the Imagio ultrasound component will be displayed for 2% POM and assessed using 99% confidence bounds.

Additionally, sensitivity and specificity results will be separately displayed for Imagio and the Imagio ultrasound component for the pre-defined subpopulations as descriptive statistics.

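### Sections 6.4.1 and 6.7 define the negative likelihood ratio as the reciprocal of the correct form given in section 8.5

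*Protocol*

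**What the plan says.** The protocol defines the negative likelihood ratio (NLR) in three places.

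- Section 6.4.1, item 5: "Negative likelihood ratio (NLR = Sp/(1-Se", that is, Sp/(1-Se).
- Section 6.7, in the list of selected endpoints: "negative likelihood ratio (Sp/ (1-Se", the same expression.
- Section 8.5: "The negative likelihood ratio is defined as (1 TPR)/(1 FPR". No minus signs appear in the text copy read here. I take them as lost in conversion from PDF, so the formula is (1-TPR)/(1-FPR). The missing signs are not part of this point.

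Section 8.5 also fixes the terms: "The true positive rate (TPR) or sensitivity of the test is defined as TP/ (TP + FN" and "The specificity of the test is defined as TN/ (TN + FP".

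Section 8.7.4 makes the NLR a reported output at the 2% probability-of-malignancy threshold, assessed with 99% confidence bounds: "concordance, PPV, NPV, PLR, NLR, and odds ratio for Imagio and the Imagio ultrasound component will be displayed". It does not say which of the definitions applies.

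**The concern.** A likelihood ratio for a negative result compares how often the test is negative in cancers with how often it is negative in benign masses. For a useful test it lies below 1, and smaller is better. Sp/(1-Se) has the two rates the other way up, so a good test scores well above 1 and larger becomes better.

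Because the wrong expression appears twice, once under a heading that announces statistical endpoints, a programmer or report author could take it as the definition. The displayed NLR for both image sets would then be inverted. A reader who assumed the usual meaning would conclude that a negative read raises the odds of cancer, and would rank Imagio and IUS in the wrong order on this metric.

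**Working it through.** The protocol states no numerical NLR, so there is no figure to reproduce. The check is on the formula.

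**Step 1: derive the NLR from the 2x2 table in section 8.5.**

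NLR = P(test negative | cancer) / P(test negative | benign) = [FN/(TP+FN)] / [TN/(TN+FP)] = (1-Se)/Sp.

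Since TPR = Se and 1-FPR = Sp, this equals (1-TPR)/(1-FPR), so section 8.5 is correct. Sections 6.4.1 and 6.7 give Sp/(1-Se), and [Sp/(1-Se)] × [(1-Se)/Sp] = 1. They state the exact reciprocal.

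The conflict does not hinge on the lost minus signs: the sensitivity term is in the numerator in 8.5 and in the denominator in 6.4.1 and 6.7.

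**Step 2: check against the other items in 6.4.1.**

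Item 4 reads "Positive likelihood ratio (PLR = Se/(1-Sp", which agrees with TPR/FPR in 8.5. Item 8 defines the odds ratio as (TP/FP)/(FN/TN), the same in both sections. From the 2x2 table, the odds ratio must equal PLR/NLR.

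Inputs: Se 95% and Sp 45%, the alternative values in Tables 9 and 8 of section 8.6.

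- PLR = 0.95/(1-0.45) = 1.727
- OR = [0.95/0.55] / [0.05/0.45] = 15.55
- With NLR from 8.5: 0.05/0.45 = 0.111, and 1.727/0.111 = 15.55, which matches the OR.
- With NLR from 6.4.1: 0.45/0.05 = 9.0, and 1.727/9.0 = 0.19, which does not.

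So item 5 is inconsistent with items 4 and 8 of its own list.

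**Step 3: size at the protocol's planning values.**

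| Se | Sp | Source of the values | 8.5: (1-Se)/Sp | 6.4.1 and 6.7: Sp/(1-Se) |
|---|---|---|---|---|
| 95% | 45% | alternatives, Tables 9 and 8 | 0.05/0.45 = 0.111 | 0.45/0.05 = 9.0 |
| 90% | 40% | nulls of Hypotheses 4 and 3 | 0.10/0.40 = 0.25 | 0.40/0.10 = 4.0 |

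**Step 4: direction of the device comparison.**

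Assume, for illustration, equal sensitivity of 95%, Imagio specificity 45%, and IUS specificity 6 points lower (the advantage in Hypothesis 1), so 39%.

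- Correct form: Imagio 0.05/0.45 = 0.111, IUS 0.05/0.39 = 0.128. The better device has the smaller value.
- 6.4.1/6.7 form: Imagio 0.45/0.05 = 9.0, IUS 0.39/0.05 = 7.8. The better device has the larger value.

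**Step 5: what the inverted value would mean if used as a likelihood ratio.**

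Take the breast cancer detection range of 18% to 40% in section 8.1.1 as illustrative prevalence, with Se 95% and Sp 45%. Post-test odds = prior odds × NLR.

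- Prevalence 18%: prior odds 0.18/0.82 = 0.2195. With 0.111 the post-test probability is 2.4%, which equals 1-NPV. With 9.0 it is 66%.
- Prevalence 40%: prior odds 0.40/0.60 = 0.667. With 0.111 it is 6.9%, again equal to 1-NPV. With 9.0 it is 86%.

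The inverted figure would make a negative result appear to raise the risk of cancer.

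**The case against.** The case for leaving this alone rests on four arguments.

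**The operative section is right.** A reader might infer that the reported NLR will be the reciprocal of the true value. The protocol does not support that. The correct form is in section 8.5, inside the statistical methods, in a list of endpoints to be assessed for each image set. Section 8.7.4, which displays the NLR, is in the same part, and section 9.12 says the analysis plan is to follow the statistical section. This stands: the inversion follows only if the 6.4.1/6.7 wording is the one programmed. It does not remove the contradiction, because no sentence expressly ranks 8.5 above a section titled as the statistical endpoints.

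**The NLR does not carry the biopsy-sparing claim.** A reader might infer that it is the figure behind that claim. No section gives it this role. The rationale in 1.4 runs through a reduced probability of malignancy and BI-RADS downgrading, Hypothesis 1 through specificity, and Hypothesis 5 through downgrading. The objectives name PPV and NPV. In 6.7 the NLR is one of several endpoints listed together. This stands in full.

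**Nothing confirmatory depends on it.** The NLR has no hypothesis, success threshold or power calculation, and no role in the sample size re-estimation. This also stands.

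**The error is recoverable.** Sensitivity, specificity, PLR and odds ratio are displayed alongside, and a reciprocal with its bounds can be inverted exactly, the lower and upper bounds changing places. That limits the harm, but is no reason to leave a wrong formula in place.

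**Conclusion.** The formula in 6.4.1 item 5 and in 6.7 is wrong as written: it is the reciprocal of the negative likelihood ratio, it contradicts 8.5, and it breaks the relation between the other items in its own list. This is an algebraic error and not a choice of convention.

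The consequence is conditional. Only if the 6.4.1/6.7 form were used would the displayed NLR and its 99% bounds be inverted and the Imagio-IUS ordering on this metric reversed. The factor-of-reciprocal result holds at any sensitivity and specificity; the particular values rest on the planning figures in sections 8.2 and 8.6.

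Hypotheses 1 to 6, the sample size, the primary specificity test and the secondary sensitivity test are untouched. The point is minor.

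**What to change.** In section 6.4.1, item 5, and in section 6.7, replace Sp/(1-Se) with (1-Se)/Sp, so that both agree with section 8.5. No other definition in those lists needs to change on this account.

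The cost is a text correction in two places. It alters no data collection, design, power or analysis.
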